#### Eligibility Criteria:

258 259

- 1. Age 3 to <13 years at the time of randomization
- 2. Amblyopia associated with anisometropia, strabismus, or both
  - o Criteria for strabismic amblyopia: At least one of the following must be met:
    - Presence of a heterotropia on examination at distance or near fixation (with or without optical correction)
    - Documented history of strabismus which is no longer present (which in the judgment of the investigator could have caused amblyopia)
  - o Criteria for anisometropia: At least one of the following criteria must be met:
    - ≥1.00 D difference between eyes in spherical equivalent (SE)
    - ≥1.50 D difference in astigmatism between corresponding meridians in the two
  - o Criteria for combined-mechanism amblyopia: Both of the following criteria must be
    - Criteria for strabismus are met (see above)
    - ≥1.00 D difference between eyes in spherical equivalent OR ≥1.50 D difference in astigmatism between corresponding meridians in the two eyes
- 3. No previous treatment for amblyopia, including total spectacle wear as specified below:
  - a. No more than 72 hours of spectacle wear if spectacle wear attempted more than 3 months prior to the Enrollment Visit
  - b. No more than 24 hours of spectacle wear if spectacle wear attempted less than 3 months prior to the Enrollment Visit.

- 4. Investigator planning to initiate (or has already prescribed) spectacle correction of refractive error meeting the following criteria based on a cycloplegic refraction that has been performed within 45 days of the Enrollment visit **and** within 90 days of the Spectacle Baseline visit:
  - a. Full correction of spherical and cylindrical anisometropia.
  - b. Full correction of astigmatism with the same axis found by the cycloplegic refraction.
  - c. Allow symmetric reduction of sphere up to 1.50, prescribing such that the most hyperopic meridian is not rendered myopic, in the non-amblyopic eye at baseline.
  - d. Allow symmetric addition of only -0.25 sphere for participants with plano sphere, spherical myopia, simple or compound myopic astigmatism in the non-amblyopic eye at baseline.
  - 5. For participants not already prescribed spectacles meeting eligibility criteria prior to enrollment, a single measurement of best-corrected VA in each eye, measured using the investigator's preferred VA testing method, must meet the criteria specified below. The refractive correction should correct for the full cycloplegic refractive error if the child is cyclopleged. If the child is not cyclopleged, the refractive correction should meet the refractive error prescribing criteria specified in Section 2.3 #4.
    - VA in the amblyopic eye approximately 20/40 to 20/200 (0.26 to 1.04 logMAR inclusive, 33 to 72 letters inclusive)
    - Age-normal VA in the fellow eye:
      - o 3 years: approximately 20/50 or better,  $\leq$  0.44 logMAR,  $\geq$  63 letters
      - 4 years: approximately 20/40 or better,  $\leq$  0.34 logMAR,  $\geq$  68 letters
      - 5-6 years: approximately 20/32 or better,  $\leq$  0.24 logMAR,  $\geq$  73 letters
      - o 7-12 years: approximately 20/25 or better,  $\leq 0.14 \log MAR$ ,  $\geq 78 \log MAR$
    - Interocular difference  $\ge 3 \log MAR$  lines (0.3 logMAR) or  $\ge 15$  letters
    - When participants return for the Spectacle Baseline / Randomization Visit with their new spectacles, they will need to meet the same criteria as above using the ATS-HOTV or E-ETDRS protocol after wearing the new spectacles for at least 10 minutes (based upon the mean of a test and retest of VA in those new spectacles).
  - 6. Investigator is willing to prescribe spectacle wear followed sequentially by patching or simultaneous spectacles and patching treatment per protocol.
  - 7. Parent and participant willing to forego option of contact lens wear for the duration of the study.
  - 8. Parent understands the protocol and is willing to accept randomization.
  - 9. Parent has phone (or access to phone) and is willing to be contacted by Jaeb Center staff or other study staff.
  - 10. Relocation outside of area of an active PEDIG site for this study within the next 56 weeks is not anticipated.

## 2.4 Participant Exclusion Criteria

284

285

286 287

288

289

290

291292

293

294

295

296

297

298

299

300 301

302

303 304

305

306

307 308

309

310311

312

313314

315

316

317318

319

320321

322323

324 325

- Individuals meeting any of the following exclusion criteria at baseline will be excluded from study participation.
  - 1. Myopia greater than -6.00D spherical equivalent in either eye.

- 326 2. Previous intraocular or refractive surgery.
  - 3. Planned strabismus surgery in the next 56 weeks.
  - 4. Any previous treatment for amblyopia (patching, atropine, Bangerter filter, vision therapy, or binocular treatment).
  - 5. Previous spectacle or contact lens wear as specified below:
    - More than 72 hours of total spectacle wear time if attempted 3 months or more prior to the Enrollment Visit
    - More than 24 hours of total spectacle wear time if attempted less than 3 months prior to the Enrollment visit.
  - 6. Parent and participant unwilling to forego option of contact lens wear for the duration of the study.
  - 7. Ocular co-morbidity that may reduce VA determined by an ocular examination performed within the past 7 months (Note: nystagmus per se does not exclude the participant if the above VA criteria are met).
  - 8. Severe developmental delay that would interfere with treatment or evaluation (in the opinion of the investigator). Participants with mild speech delay or reading and/or learning disabilities or ADHD are not excluded.
  - 9. Known allergy to adhesive patches.
  - 10. Known allergy to silicone.

344 345

327

328 329

330

331

332

333

334

335

336

337

338

339

340

341

342

343

#### 2.5 **Screening Examination Procedures**

346 347 348

#### 2.5.1 Historical Information

Historical information elicited will include the following: date of birth, sex, race, ethnicity, and prior amblyopia therapy (e.g., spectacles, contact lenses, patching, pharmacologic, filters).

350 351 352

349

# 2.5.2 Visual Acuity Testing for Participants Prescribed Spectacles at Time of Enrollment

353 For participants not already prescribed spectacles meeting eligibility criteria prior to enrollment, 354 visual acuity will be tested once in each eye at the Enrollment Visit using the investigator's

- **preferred method.** VA will be tested with or without cycloplegia, using a trial frame or through 355
- the phoropter. The refractive correction should correct for the full cycloplegic refractive error if 356
- 357 the child is cyclopleged. If the child is not cyclopleged, the refractive correction should meet the
- 358 refractive error prescribing criteria specified in Section 2.3 #4. This VA test at the Enrollment
- 359 visit will be done to determine whether the presenting VA deficit is likely to be primarily optical
- 360 blur or primarily amblyopia. The final determination of VA eligibility will be made at the
- 361 Spectacle Baseline Visit after the participant has worn his/her new spectacles for a minimum of 10 minutes (based upon the mean of a test and retest of VA in those new spectacles). 362

363

364 Potential participants who do not meet VA criteria in trial frames or phoropter (section 2.3) will 365 not be eligible to participate in the study and will not return for the Spectacle Baseline / Randomization Visit.

366

367 368

369

370

Potential participants meeting the VA criteria with their prescription in trial frames or phoropter and who appear to meet other eligibility criteria may be offered participation in the study, in which case the current visit would become the Enrollment Visit. Alternatively, the child may

371 return on a subsequent day for the Enrollment Visit.

373	All eligible participants will return for a Spectacle Baseline / Randomization Visit within 45
374	days (after collecting their spectacles from the optical shop but having been instructed not
375	to wear the spectacles before the Spectacle Baseline / Randomization Visit).
376	Spectacles will be paid for by the study with the expectation that the majority of participants who
377	appear eligible at the Enrollment Visit will still be eligible at the Spectacle Baseline /
378	Randomization Visit.
379	
380	2.5.3 Obtaining Spectacles
381	Study spectacles will be either be picked up by the participant prior to the Spectacle Baseline /
382	Randomization Visit (with instructions not to wear) or sent directly to the Investigator. If picked
383	up from the optical shop, the new spectacles should be carried to the office between pickup and
384	the Spectacle Baseline / Randomization Visit and should not be worn for more than a total of 24
385	hours prior to the Spectacle Baseline / Randomization Visit.

372

# **CHAPTER 3.** Spectacle Baseline Visit / Randomization

#### 3.1 Spectacle Baseline / Randomization Visit

The purpose of the Spectacle Baseline / Randomization Visit is to confirm eligibility for the randomized trial with the participant wearing his or her new spectacle correction for the first time. The Spectacle Baseline / Randomization Visit should occur within 45 days of the Enrollment visit and is the visit at which eligible participants will be randomly assigned to either Sequential or Simultaneous treatment.

If the Spectacle Baseline / Randomization Visit does not occur within 45 days of the Enrollment visit, all Eligibility criteria (*section 2.3*) will need to be reconfirmed.

Prior to the visit, the office staff should verify that the spectacles prescribed at the Enrollment visit either have already been received at their office or that the participant will be picking their spectacles up by the day of the Spectacle Baseline / Randomization Visit.

Informed consent will have been previously obtained at the Enrollment Visit.

Participants who have worn their spectacles for more than a total of 24 hours prior to the Spectacle Baseline / Randomization Visit will not be eligible and study participation will end.

At the visit, the spectacle prescription should be verified with a lensometer. Sphere and cylinder power must meet the criteria in *section 2.3*.

#### 3.1.1 Lensometry

- When the participant returns with their new spectacles for the Spectacle Baseline /
- Randomization Visit the spectacles will need to meet the following criteria compared with the prescribed refractive correction:
  - Sphere power must be within 0.25 D of the prescribed correction.
  - Cylinder power must be within 0.25 D of the prescribed correction.
  - Axis must be within +/- 10 degrees if cylinder power is ≤1.00D, and within +/- 5 degrees if cylinder power is >1.00D.

If these criteria are not met, the spectacles must be re-made by the optical lab and the participant will return within another 45 days for the Spectacle Baseline / Randomization Visit (see *section 2.3*). **Note:** The cycloplegic refraction meeting the Enrollment criteria (see *section 2.3 #4*) must have been performed within 90 days of the repeat Spectacle Baseline Visit. Otherwise, the participant will require repeat cycloplegic refraction to confirm that the spectacle prescription is still within study tolerances before the Spectacle Baseline visit can be conducted.

The PedEyeQ child questionnaire (or proxy questionnaire) and parent questionnaire should be completed before any clinical testing.

[figure not shown]
#### 3.1.2 Visual Acuity Testing

- Distance VA testing, with the participant wearing his/her new spectacle correction, will be
- performed in each eye by a certified examiner using the electronic ATS-HOTV VA protocol for

432 children <7 years and the E-ETDRS VA protocol for children ≥ 7 years on a study-certified 433 acuity tester displaying single surrounded optotypes as described in the ATS Testing Procedures 434 Manual. 435 436 Participants should wear the new spectacles for at least 10 minutes before visual acuity is tested. 437 After an initial test of distance VA, distance VA will be retested, because study VA will be based 438 on the mean of test and retest at each visit. 439 440 3.1.2.1 **Management of Reduced Visual Acuity** 441 442 If the investigator suspects incomplete relaxation of accommodation in the current 443 spectacles is causing reduction of the mean of test and retest VA at the Spectacle Baseline 444 visit from the Enrollment visit in either eye (regardless of whether this initial VA 445 measurement renders the participant eligible or ineligible), the investigator should consider (not mandatory) repeating test and retest VA with a -1.00 D lens in BOTH eyes, regardless of 446 447 refractive error. 448 If the participant meets eligibility criteria based on mean of test and retest VA through the 449 -1.00 D lens, the investigator has two options: 450 1. Randomize the participant in the current spectacles (the test and re-test VA using the -1.00 D lens will be used as the participant's baseline VA) 451 452 2. Change the spectacles by reducing the hyperopic power up to a symmetrical reduction of 453 1.50 D sphere, following guidelines in section 2.3 (#4). 454 If the participant does not meet eligibility criteria based on mean of test and retest VA, the participant will be dropped from the study. 455 If the investigator suspects that a change in refractive error is causing reduction of the 456 457 mean of test and retest VA at the Spectacle Baseline visit from the Enrollment visit in either eye (regardless of whether this initial VA measurement renders the participant 458 459 eligible or ineligible), the investigator should consider (not mandatory) repeating cycloplegic refraction. 460 461 If the current spectacles are not within the lensometry tolerances specified in the protocol (section 3.1.1) based on the new cycloplegic refraction, the spectacles should be re-made and 462 will be paid for by the study. An investigator may repeat visual acuity testing at their discretion 463 464 to determine if a participant still meets the VA eligibility requirements to continue in the study, 465 but this is not mandatory. The participant should not wear any glasses until they return for another Spectacle Baseline / Randomization visit within 45 days. 466 467 If the current spectacles **are** within the lensometry tolerances and the participant meets eligibility

criteria, the participant may be randomized.

468

#### 3.1.2.2 Other Spectacle Change Allowances

If the investigator identifies a new problem at the time of the Spectacle Baseline visit (e.g., new manifest strabismus) that could be appropriately managed by a change in spectacle correction, re-make of the glasses by the optical lab is permitted and will be paid for by the study, as long as the new spectacle prescription is within the refractive error requirements of the protocol, as specified in section 2.3 #4. The participant should return for another Spectacle Baseline / Randomization visit within 45 days.

#### 3.1.3 Testing in New Spectacles

Participants will wear their prescribed spectacles for the first time for at least 10 minutes prior to testing. Participants who have worn their spectacles for more than a total of 24 hours prior to

482	this visit will end study participation. Participants who have worn their spectacles for less than
483	24 hours will have their VA measured twice while wearing their new spectacles.

484

- 485 If all components of the Spectacle Baseline / Randomization visit are not completed, the child 486 may return within 7 days to complete the remaining study procedures or repeat all study 487 procedures (at investigator discretion) and be randomized (NOT wearing the glasses in the 488 meantime). If returning more than 7 days later, all testing must be repeated at a new Spectacle
- 489 Baseline / Randomization visit (NOT wearing the glasses in the meantime).
  - The order of testing follows (additional details are described in the *ATS Testing Procedures Manual*):

492493

490

491

#### 1. PedEyeQ:

495 496

497

494

498 499 500

501

502 503

505 506

504

507508

509510511

513514

515

512

516517519

518519520

521

522523

524525526

The PedEyeQ is a patient-derived questionnaire designed to assess functional vision and eye-related quality of life. It consists of a child questionnaire for children ages 5 years and older, a proxy questionnaire completed by the parent regarding their child, and a parent questionnaire regarding the parent's own quality of life. The child questionnaire is administered by study personnel to children under the age of 8 years and is completed by the child for children 8 years of age or older (with the help of study personnel, if needed). Proxy and Parent questionnaires are completed by the parent. The questionnaires take about 10 minutes to complete.

## 2. Distance VA Testing:

- Monocular distance VA testing will be performed in refractive correction in each eye by a certified examiner using the electronic ATS-HOTV VA protocol for children <7 years and the E-ETDRS VA protocol for children ≥ 7 years on a study-certified acuity tester displaying single surrounded optotypes.
- The VA protocol used at enrollment will be used throughout the study regardless of age at follow-up.
- 2. Repeat Distance VA Testing: Monocular distance VA testing will be performed in current refractive spectacle correction in each eye by a certified examiner (as above).

## 3. Binocularity Testing:

- Gross binocularity will be tested in current spectacle correction at near using the hand-held Worth 4-Shape test held at 40 cm.
- Stereoacuity will be tested at near in current spectacle correction using both the Randot Butterfly and Randot Preschool stereoacuity tests.

## 4. Ocular Alignment Testing:

• Ocular alignment will be assessed in current spectacle correction by the cover test, simultaneous prism and cover test (SPCT) (in cases of strabismus detected by cover test), and prism and alternate cover test (PACT) in primary gaze at distance (3 meters) and at near (1/3 meter).

## 5. Contrast Sensitivity Testing

• Contrast sensitivity will be assessed in each eye (right eye first then left eye) using the SpotChecks™ Contrast Sensitivity Test. Contrast Sensitivity testing should be performed last prior to randomization.

527

3.2 Randomization

528	For each age cohort, the Jaeb Center will construct a Master Randomization List using a			
529	permutated block design stratified by VA in the amblyopic eye (calculated as a mean of the test			
530	and retest) as moderate 20/40 to 20/80 (53 to 72 letters; 0.26 to 0.64 logMAR) versus severe			
531	20/100 to 20/200 (33 to 52.5 letters; 0.65 to 1.04 logMAR) which will specify the order of			
532	treatment group assignments.			
533				
534	All eligible participants enrolled in the study will be followed for up to 56 weeks. Participants			
535	eligible for randomization will be randomly assigned within each age cohort in a 1:1 allocation			
536	to one of the following treatment groups:			
537				
538	1. Sequential treatment : full-time spectacle correction first, with subsequent patching for 2			
539	hours per day/7 days per week only if needed (no improvement (stable/worsening) and			
540	residual)			
541	2. Simultaneous treatment: full-time spectacle correction and part-time patching for 2			
542	hours per day/7 days per week			
543				
544	Once a participant is assigned to a treatment group, the participant will be included in the			
545	analysis regardless of whether or not the assigned treatment is received. Thus, the investigator			
546	must not enroll and randomize a child unless convinced that the parent will accept either			
547	treatment.			

# 548 CHAPTER 4. Randomized Trial Procedures

## 4.1 Sequential Spectacles (and Patching if Needed)

and continue to wear their spectacle correction full-time.

Participants randomized to the sequential group will initially be treated with spectacle correction to be worn all waking hours (spectacles confirmed at the Spectacle Baseline / Randomization Visit in accordance with the criteria in *section 2.3*).

Adherence with spectacle wear will be monitored throughout the study by a parental calendar.

Participants will continue to wear their spectacles as their only treatment and return for scheduled follow-up visits until non-improvement of VA (i.e., "stable/worsening") is reached or participants reach the final 56-week visit (section 4.3.3). Once VA non-improvement ("stable/worsening") has been reached, if the participant has a residual interocular difference in distance VA of more than 1 logMAR line (meeting the definition for "stable residual," section 4.3.6), the participant will start patching the non-amblyopic eye 2 hours per day/7 days per week

- Adherence with patching will be monitored throughout the remainder of the study by an occlusion dose monitor (ODM) worn on the inside of the patch.

Once patching treatment has been initiated, participants in the sequential patching group will continue follow-up every 8 weeks until no further improvement ("stable/worsening") has been reached (see *section 4.3* below) or until 56 weeks.

If there has been no further improvement in VA, but the participant has residual amblyopia ("stable residual"), treatment will be at investigator discretion but participants will continue 8-weekly visits until 56 weeks.

If non-improvement ("stable/worsening") is reached AND amblyopia is no longer present (less than or equal to 1 logMAR line) (meeting the definition for "stable resolved", *section 4.3.5*), participants will continue spectacle wear and 8-weekly visits until 56 weeks.

In participants who meet the definition of stable resolved, but amblyopia recurs (defined as a 2 or more logMAR line decrease in VA from the level measured at the visit when the definition of "stable resolved" was last met) prior to the 56-week visit, they will be treated and the method of treatment will be at investigator discretion.

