Primary Endpoint	
 
The primary efficacy endpoint will be mean change in amblyopic eye logMAR distance VA between randomization and VA at completion of randomized treatment or at 56 weeks, whichever is earlier.
 
The primary endpoint for each participant is defined as:
 
1. Amblyopic eye VA (calculated as mean of test and retest) at the last visit that was the basis for a "stable resolved" or "stable residual" determination (in the sequential group, stable residual amblyopia criteria can be reached only after patching has been instituted); or
 
2. Amblyopic-eye VA at 56 weeks (calculated as mean of test and retest) in those completing a 56 week visit without ever meeting criteria for "stable resolved" or "stable residual" amblyopia (if retest missing at 56 weeks, the single test value will be used).
 
To determine if the following endpoints differ between simultaneous treatment and sequential
 

Secondary Objectives/Endpoints	treatment groups.  Efficacy:  Child and parental health-related quality of life (HRQOL) domain scores as measured by PedEyeQ.  Proportion of participants with improvement of amblyopic eye distance VA of 2 or more logMAR lines (>=10 letters if E-ETDRS), using the primary endpoint as defined above.  Time to stable resolved amblyopia.  Amblyopic-eye distance VA (calculated as mean of test and retest) after 8 weeks.  Amblyopic-eye distance VA (calculated as mean of test and retest) at 56 weeks for all participants.  Binocularity by Randot Preschool Stereotest, Randot Butterfly Stereotest, and Worth 4 Shape Testing.  Monocular contrast sensitivity.  Safety:  Worsening of best-corrected fellow-eye distance VA of 0.2 logMAR lines or more at any time during the study from baseline (based on mean of test and retest, or initial test if retest not done).  Proportion of participants who develop a new strabismus.

	Proportion of participants who develop mild moderate and severe skin imitation from
	
 
Proportion of participants who develop mild, moderate, and severe skin irritation from patching.
 

	To evaluate the following endpoint within simultaneous treatment and sequential treatment groups:
	Recurrence of amblyopia in those who have resolved (defined as a 0.2 or more logMAR reduction and IOD of 0.2 logMAR or more from value at visit of resolution).

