## 4.3 Amblyopia Status

- At each follow up visit, the website will determine if a participant is no longer demonstrating
- 614 improvement of visual acuity ("stable/worsening"). If a participant is no longer improving in
- visual acuity ("stable/worsening"), amblyopia status will then be defined as residual or resolved
- to direct the next step in randomized treatment, as described in 4.1 and 4.2. The subsections
- below provide the study definitions of VA improvement, VA non-improvement
- 618 ("stable/worsening"), and the criteria for determining amblyopia status (residual, resolved,
- 619 recurrent).

606 607

608

609

610

611 612

627 628

634

637

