## 4.3.8 Recurrent Amblyopia

Recurrent amblyopia is defined as a decrease in amblyopic eye VA of 0.2 logMAR or more and a 0.2 logMAR or more interocular difference of distance VA between the amblyopic eye and the non-amblyopic eye on a subsequent visit to the visit at which the definition of "stable resolved" was met. VA is calculated for each eye as the mean of the test and retest VA measurements

made at the visit. If VA is not tested twice at a specific visit, then the change in VA will not be evaluated until the next study follow-up visit.

Participants meeting the definition for "Recurrent amblyopia" should be treated, and the method of treatment will be at investigator discretion.

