#### 4.4.2 Unscheduled Visits

Investigators may schedule additional visits at their own discretion. Participants will continue to follow the study-specified follow-up schedule regardless of any non-study visits. No data will be collected at non-study visits for the purpose of the study. Data from non-study visits will not be used to determine VA non-improvement ("stable/worsening") or whether the amblyopia is resolved or residual.

803 804

Investigators must not start any additional treatment (other than that outlined in *section 4.1 and 4.2*) prior to the 56-week outcome visit.

**CHAPTER 5.** Miscellaneous Considerations

808	
809	5.1 Contacts by the Jaeb Center for Health Research and Sites
810	The Jaeb Center serves as the PEDIG Coordinating Center. The Jaeb Center will be provided
811	with the parent's contact information. The Jaeb Center may contact the parents of the
812	participants. Permission for such contacts will be included in the Informed Consent Form. The
813	principal purpose of the contacts will be to develop and maintain rapport with the participant and
814	family and to help coordinate scheduling of the outcome examinations.
815	
816	5.2 Spectacles
817	Participants who have been screened and meet eligibility criteria while wearing trial frames with
818	the cycloplegic refraction at the screening exam will be provided spectacles paid for by the
819	study.
820	
821	Any change of spectacles will be paid for by the study.
822	
823	Contact lenses are not allowed during the study.
824	
825	5.3 Management of Strabismus
826	Strabismus surgery may be performed after the participant has been released to non-study
827	treatment. If surgery is performed, the date and type of surgery will be recorded in the comment
828	section of the Follow-up Examination Form. Note that participants should not be enrolled in the
829	study if strabismus surgery is planned or desired by families in the next 56 weeks (see exclusion
830	criteria section 2.4).
831	
832	5.4 Risks
833	
834	5.4.1 Risks of Examination Procedures
835	The procedures in this study are part of daily eye care practice in the United States and pose no
836	known risks. As part of a routine usual-care exam, the participant may receive
837	cycloplegic/dilating eye drops.
838	
839	5.4.2 Risks of Patching
840	If skin irritation occurs, the parent will be advised to put an emollient on the skin and discontinue
841	use of the patch for a day.
842	

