## 6.8 Recurrence of Amblyopia

The proportion of participants who meet criteria for stable resolved and then have a recurrence of amblyopia will be tabulated within each treatment group and an exact 2-sided 95% confidence interval will be computed on the proportion within each treatment group.

1171 1172 1173

1174

1175

1176

Recurrent amblyopia is defined as a decrease in amblyopic eye VA of 0.2 logMAR or more and a 0.2 logMAR or more interocular difference of distance VA between the amblyopic eye and the non-amblyopic eye on a subsequent visit compared to the visit at which the definition of "stable resolved" was met. VA is calculated for each eye as the mean of the test and retest VA measurements made at the visit.

1177 1178 1179

1185

1186

1187

1188 1189

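### Sections 4.1 and 4.2 tell sites to treat recurrent amblyopia on a 2-line VA loss alone, while 4.3.8, 6.8 and the summary also require an interocular difference of 0.2 logMAR or more

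*Protocol*

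**What the plan says.** Sections 4.1 (sequential) and 4.2 (simultaneous) carry the same sentence. It applies when "amblyopia recurs (defined as a 2 or more logMAR line decrease in VA from the level measured" at the visit where stable resolved "was last met) prior to the 56-week visit, they will be treated and the method of treatment will be at investigator discretion". No fellow-eye or interocular condition appears, and there is no reference to 4.3.8.

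The other places that define recurrence have two parts:

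- Section 4.3.8 requires "a decrease in amblyopic eye VA of 0.2 logMAR or more and a 0.2 logMAR or more interocular difference" between the eyes, and then gives its own instruction to treat at the investigator's discretion.
- Section 6.8, the analysis definition, has the same two parts, assessed "on a subsequent visit compared to the visit at which the definition of" stable resolved was met.
- The Protocol Summary has it "defined as a 0.2 or more logMAR reduction and IOD of 0.2 logMAR or more from value at visit of resolution".

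Two further passages bear on which rule governs. Section 4.3 says that its subsections give the study definitions, recurrent status included, and that residual or resolved status serves "to direct the next step in randomized treatment, as described in 4.1 and 4.2". Section 4.4.2 says "Investigators must not start any additional treatment (other than that outlined in" sections 4.1 and 4.2) before the 56-week visit.

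**The concern.** Amendment 5 added the interocular condition because a fall in amblyopic-eye acuity alone can reflect poor attention, cooperation or motivation that affects both eyes. It names 4.3.8 and 6.8 as the sections holding the old one-part definition. Sections 4.1 and 4.2 are not named and still state that one-part rule, which fits their having been overlooked.

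These two sections are operative treatment instructions. A site that follows them literally must treat some children whom the amended definition was written to exclude. What is at stake is unneeded treatment of individual children, and some extra treatment entering secondary comparisons made at the end of follow-up. Those are amblyopic-eye acuity at week 56, which the summary lists as "Amblyopic-eye distance VA (calculated as mean of test and retest) at 56 weeks for all participants", and the 56-week PedEyeQ domain scores in 6.5.1.

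A smaller mismatch sits beside it. Sections 4.1 and 4.2 measure the fall from the visit where stable resolved was last met. Sections 4.3.8 and 6.8 refer to the visit where it was met, without saying first or last.

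**Working it through.** The protocol gives no figure to reproduce, so the check compares the rules and finds where they disagree.

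**Inputs**
- Resolved amblyopia: IOD of 0.1 logMAR or less (4.3.4).
- Rule A (4.1, 4.2): decrease of at least 2 lines, that is 0.20 logMAR. The eye is not named; I take it to be the amblyopic eye.
- Rule B (4.3.8, 6.8, summary): amblyopic-eye decrease of at least 0.20 and IOD of at least 0.20.

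**Formula.** Let d be the signed IOD at the stable-resolved visit (positive when the amblyopic eye is worse), a the later loss in the amblyopic eye and f the later loss in the fellow eye, all in logMAR. Then:

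- later IOD = d + a − f
- Rule A is met when a ≥ 0.20
- Rule B is met when a ≥ 0.20 and d + a − f ≥ 0.20
- the rules conflict when a ≥ 0.20 and f > d + a − 0.20

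At a = 0.20 exactly, the conflict condition becomes f > d, where d is at most 0.10. This form does not depend on the scoring step of the acuity test, so it applies to both age cohorts.

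**Illustrations (assumed values, amblyopic/fellow logMAR)**

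| At stable resolved | Later visit | d | a | f | Later IOD | 4.1/4.2 | 4.3.8/6.8 |
|---|---|---|---|---|---|---|---|
| 0.10/0.10 | 0.30/0.30 | 0.00 | 0.20 | 0.20 | 0.00 + 0.20 − 0.20 = 0.00 | treat | not recurrent |
| 0.05/0.10 | 0.25/0.10 | −0.05 | 0.20 | 0.00 | −0.05 + 0.20 − 0.00 = 0.15 | treat | not recurrent |
| 0.15/0.10 | 0.35/0.10 | 0.05 | 0.20 | 0.00 | 0.05 + 0.20 − 0.00 = 0.25 | treat | recurrent |

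The first row is the situation Amendment 5 set out to exclude. The second shows that the conflict can arise with no fellow-eye change when the amblyopic eye was slightly the better one at resolution. The Amendment 3 rationale expects some children whose amblyopic eye is no longer the worse one at the outcome visit. In the third row the rules agree.

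**Reference visit.** Take 0.00/0.00 (stable resolved), then 0.10/0.00 (no improvement and IOD 0.10, so stable resolved again), then 0.20/0.00. Measured from the first such visit, the loss is 0.20 − 0.00 = 0.20 with IOD 0.20, so the child is recurrent under rule B. Measured from the last, the loss is 0.20 − 0.10 = 0.10, so the child is not recurrent under either rule. This matters only for children who meet stable resolved more than once.

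**The case against.** The best defence is that the intended rule is plain. Section 4.3 presents its subsections as the source of the study definitions and includes recurrence among them. Section 4.3.8 holds both the correct definition and the instruction to treat. Amendment 2 aligned the flow chart with 4.3.8 on treating recurrence, so the sponsor already used that section as the reference. This settles the intent. It does not remove the wrong instruction: nothing says that 4.3 overrides 4.1 and 4.2, those sections cite 4.3.5 for stable resolved but give their own rule for recurrence, and 4.4.2 points to them for permitted treatment. Amendment 3 corrected a similar mismatch between 4.1 and sections 4.3.3 and 4.3.4.

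The second defence is that little follows from it. Section 4.3.2 releases non-improving children who have been patching to discretionary treatment, and the Amendment 4 rationale describes treatment after the primary outcome as discretionary. Children with stable residual amblyopia already receive such treatment up to week 56. The 56-week comparisons therefore contain discretionary treatment by design, and a few more treated children would change them little. This stands and limits the size of the point. It does not justify the mismatch, because 4.1 and 4.2 keep stable-resolved children on spectacles (4.2 explicitly without patching) unless recurrence occurs.

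A reader might also count five scheduled visits (weeks 16 to 48) at which the wrong trigger could fire for a child stable resolved at week 8. That is a near-empty case. Baseline IOD is at least 0.30, non-improvement means a gain below 0.05, and resolution needs an IOD of 0.10 or less, so the fellow eye would have to worsen by more than 0.30 − 0.05 − 0.10 = 0.15. No exposure count is relied on here.

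**Conclusion.** The inconsistency is real and lies within the current protocol; the amendment log serves only to show intent. Sections 4.1 and 4.2 are wrong as written, and 4.3.8 is evidently the intended rule. It is a treatment-rule inconsistency, not a fault in the choice of analysis.

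Its effect is small. A reader might infer that the equivalence conclusion is at risk, but the documents do not support that: for a child who reaches stable resolved, the primary outcome (6.4) is taken at that determination, before any recurrence. A reader might also infer that the recurrence proportion is computed on the wrong definition. Section 6.8 carries the two-part rule, so only the unstated first-or-last reference visit touches it. Nor can bias toward one arm be claimed, because the sentence is identical in 4.1 and 4.2.

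What remains is that some children may be treated before week 56 whom the protocol does not regard as recurrent, with a possible small effect on 56-week acuity and PedEyeQ. No frequency can be given, because the protocol has no data on how often the two rules diverge. The conclusion assumes that at least some sites follow 4.1 and 4.2 as written. The flow chart is not available, so what it shows sites cannot be checked.

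**What to change.** In 4.1 and 4.2, replace the definition in brackets with a reference to the two-part definition in 4.3.8. State one reference visit, for example the visit at which stable resolved was last met, and use it in 4.1, 4.2, 4.3.8, 6.8 and the Protocol Summary. The cost is a wording amendment and a note to sites, with no new data, visits or participants.
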